7.8.11.2. Clinical Laboratory Parameters

Descriptive statistics for clinical laboratory values (in standard units) and changes from the baseline values at each assessment time point will be presented by treatment group, for each clinical laboratory parameter.

The number and percentage of patients with potentially clinically significant (PCS) post-baseline clinical laboratory values will be tabulated by treatment group for the TE period. The criteria for PCS laboratory values are described in Table 2. The percentages will be calculated relative to the number of patients with available non-PCS baseline values and at least 1 assessment in the corresponding post-baseline TE period. The numerator will be the total number of patients with available non-PCS baseline values and at least 1 PCS value in the corresponding post-baseline period. A supportive listing of patients with PCS post-baseline values will be provided, including the PID number, study center, and baseline and post-baseline values. A listing of all AEs for patients with PCS laboratory values will also be provided.

Table 2: Criteria for Potentially Clinically Significant Laboratory Results

Parameter	SI Unit	Lower Limit	Higher Limit
CHEMISTRY			
Albumin	g/L	$< 0.9 \times \text{LLN}$	$> 1.1 \times \text{ULN}$
Alanine aminotransferase	U/L	—	$\geq 3 \times \text{ULN}$
Alkaline phosphatase	U/L	—	$\geq 3 \times \text{ULN}$
Aspartate aminotransferase	U/L	—	$\geq 3 \times \text{ULN}$
Bicarbonate	mmol/L	$< 0.9 \times \text{LLN}$	$> 1.1 \times \text{ULN}$
Bilirubin, total	$\mu\text{mol/L}$	—	$> 1.5 \times \text{ULN}$
Calcium	mmol/L	$< 0.9 \times \text{LLN}$	$> 1.1 \times \text{ULN}$
Chloride	mmol/L	$< 0.9 \times \text{LLN}$	$> 1.1 \times \text{ULN}$
Cholesterol, total	mmol/L	—	$> 1.6 \times \text{ULN}$

Parameter	SI Unit	Lower Limit	Higher Limit
Creatinine	μmol/L	—	> 1.3 × ULN
Glucose	mmol/L	< 0.8 × LLN	> 1.4 × ULN
Magnesium	mmol/L	< 0.9 × LLN	> 1.1 × ULN
Phosphate	mmol/L	< 0.9 × LLN	> 1.1 × ULN
Potassium	mmol/L	< 0.9 × LLN	> 1.1 × ULN
Protein, total	g/L	< 0.9 × LLN	> 1.1 × ULN
Sodium	mmol/L	< 0.9 × LLN	> 1.1 × ULN
Urea nitrogen	mmol/L	—	> 1.2 × ULN
Uric acid	μmol/L	< 0.9 × LLN	> 1.1 × ULN

HEMATOLOGY

Basophils, absolute cell count	10 ⁹ /L	—	> 3 × ULN
Eosinophils, absolute cell count	10 ⁹ /L	—	> 3 × ULN
Hematocrit	Ratio	< 0.9 × LLN	> 1.1 × ULN
Hemoglobin	g/L	< 0.9 × LLN	> 1.1 × ULN
Lymphocytes, absolute cell count	10 ⁹ /L	< 0.8 × LLN	> 1.5 × ULN
Mean corpuscular hemoglobin	pg	—	> 3 × ULN
Mean corpuscular hemoglobin concentration	g/L	—	> 3 × ULN
Mean corpuscular volume	fL	< 0.9 × LLN	> 1.1 × ULN
Monocytes, absolute cell count	10 ⁹ /L	—	> 3 × ULN
Neutrophils, absolute cell count	10 ⁹ /L	< 0.8 × LLN	> 1.5 × ULN
Platelet count	10 ⁹ /L	< 0.5 × LLN	> 1.5 × ULN
Red blood cell count	10 ¹² /L	< 0.9 × LLN	> 1.1 × ULN
White blood cell count	10 ⁹ /L	< 0.7 × LLN	> 1.5 × ULN

LLN=lower limit of normal value provided by the laboratory; SI=*Le Système International d'Unités* (International System of Units); ULN=upper limit of normal value provided by the laboratory.

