5.1.2 Stopping Criteria and Data Monitoring Committee (DMC)

5.1.2.1 Study Drug Discontinuation Criteria for Individual Patients

A patient will be discontinued from study drug dosing in the event of a confirmed pregnancy (see Section [8.2.1.4.2](#)).

Dosing of study drug for an individual patient will be suspended for up to 5 days and a patient may be discontinued from study drug dosing for the following reasons:

- An SAE considered by the investigator or Sponsor to be related to study drug (per causality definitions in Section [8.2.1.2.2](#) and SAE definition in Section [8.2.1.1](#))
- Evidence of significant volume depletion and/or significant electrolyte abnormalities that are considered by the investigator or Sponsor to be associated with diarrhea related to study drug
- A vital sign and/or laboratory abnormality judged to be clinically significant by the investigator and that, in the opinion of the investigator or Sponsor, is related to study drug
- The occurrence of any other AE that, in the opinion of the investigator or Sponsor, is related to study drug and represents a clinically significant safety risk to the patient

The investigator will determine if the patient can continue in the study based on seriousness and severity of the AE and the patient's history. Procedures required for discontinued patients are detailed in Section [6.3](#).

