6.3 DISCONTINUATION OF PATIENTS FROM THERAPY OR ASSESSMENT

A premature discontinuation will occur when a patient who signed the ICF ceases participation in the study, regardless of circumstances, before the completion of the protocol. In addition to the individual discontinuation criteria detailed in Section 5.1.2.1, patients can prematurely discontinue or be prematurely discontinued by the investigator or Sponsor from the study at any time for any reason including the following:

- Failure to meet Inclusion/Exclusion Criteria (Screening or Pretreatment Failure)
- AE
- Lack of efficacy
- Protocol violation
- Non-compliance with study drug
- Withdrawal of consent
- Lost to follow-up (every effort must be made to contact the patient; a certified letter must be sent)
- Study termination by Sponsor
- Other, such as administrative reasons

Patients who are randomized but do not complete the Treatment Period (withdraw consent or are discontinued before they have completed 12 weeks of treatment) will be considered Treatment Period withdrawals and should complete the procedures required at the EOT Visit (even if out of window) at the time of their discontinuation. The reasons for premature discontinuation from the study will be documented on the study termination form of the eCRF. All data on the patient prior to discontinuation will be made available to Ironwood (or designee). Any patient who withdraws because of an AE will be followed until the AE resolves, stabilizes, or can be explained as being unrelated to study drug. The study centers should make a reasonable effort to follow pregnant patients until delivery or end of the pregnancy.

If a patient does not return for a scheduled termination visit (EOT Visit), the study center should contact the patient. Every effort is to be made to contact the patient, including sending a certified letter. In every case, the patient outcome, including lost to follow-up information, will be documented.

The investigator may allow a patient to stop taking study drug for up to 5 days should an intolerable AE occur. If the investigator believes that the patient is unable to resume dosing or requires a temporary suspension of dosing on more than 1 occasion, the investigator should contact the Medical Monitor to discuss the patient's continued participation in the study.

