7.8.1.1. Analysis Periods

For the purpose of analyses, three analysis periods are defined and will be used for different analyses.

The Pretreatment period is defined as the 14 days immediately prior to the date of the first dose of study drug.

The Treatment Period is defined as the period from the date of the first dose of study drug to the date of the last dose of study drug. This will be used as the primary efficacy analysis period unless otherwise specified.

The Treatment Emergent Period (TE Period) is defined as the period from the date of the first dose of study drug to 1 day after the date of the last dose. For analysis purposes, AEs and required medications will be considered treatment emergent if they occur within this period. TE period will be the primary analysis period for AEs and medications.

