7.8.11.3. Vital Signs

Descriptive statistics for vital signs (ie, pulse rate, systolic and diastolic BP, respiratory rate, temperature, and body weight) and changes from baseline at each visit and at the end of the period/study will be presented by treatment group.

The number and percentage of patients with PCS post-baseline vital signs will be tabulated by treatment group for the Treatment Emergent Period. A vital sign value will be considered PCS if it meets both the observed value criterion and the change from baseline value criterion. The criteria for PCS vital sign values is detailed in Table 3. The percentages will be calculated relative to the number of patients with available non-PCS baseline values and at least 1 assessment in the corresponding postbaseline period. The numerator will be the total number of patients with available baseline values and at least 1 PCS value in the corresponding post-baseline period. A supportive listing of patients with PCS post-baseline values will be provided, including the PID number, study center, and baseline and post-baseline values. A listing of all AEs for patients with PCS vital sign values will also be provided.

Table 3: Criteria for Potentially Clinically Significant Vital Signs

Parameter	Flag	Criteria^a	
		Observed Value	Change from Baseline
Sitting systolic blood pressure, mmHg	High	≥ 180	Increase of ≥ 20
	Low	≤ 90	Decrease of ≥ 20
Sitting diastolic blood pressure, mmHg	High	≥ 105	Increase of ≥ 15
	Low	≤ 50	Decrease of ≥ 15
Sitting pulse rate, bpm	High	≥ 120	Increase of ≥ 15
	Low	≤ 50	Decrease of ≥ 15
Weight, kg	High	—	Increase of $\geq 7\%$
	Low	—	Decrease of $\geq 7\%$

a A post-baseline value is considered potentially clinically significant if it meets both the observed-value and the change-from-baseline criteria.
 bpm=beats per minute.

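### The PCS laboratory and vital-sign tables stop at 1 day after the last dose, so a later EOT Visit value is left out, and a patient who stopped before Week 4 with no other on-period value leaves the denominator

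*SAP*

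**What the plan says.** SAP 7.8.1.1 defines the TE Period as the "period from the date of the first dose of study drug to 1 day after the date of the last dose", and names it the main period for adverse events and medications. SAP 7.8.11.2 and 7.8.11.3 then apply it to visit-based measurements. PCS "clinical laboratory values will be tabulated by treatment group for the TE period", with a denominator of patients who have "available non-PCS baseline values and at least 1 assessment in the corresponding post-baseline TE period". PCS "post-baseline vital signs will be tabulated by treatment group for the Treatment Emergent Period", with a denominator that needs at least one assessment in that same period.

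The Schedule of Evaluations (the same in both documents) has laboratory tests and vital signs on Day 1 and at Week 4 (Day 29±3), Week 8 (Day 57±3) and Week 12/EOT (Day 85+3). Week 2 is a phone call.

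Under Protocol 6.3, randomized patients who do not finish treatment "should complete the procedures required at the EOT Visit (even if out of window) at the time of their discontinuation". No maximum interval from the last dose is given. Protocol 5.1.2.1 says, for listed safety reasons, "Dosing of study drug for an individual patient will be suspended for up to 5 days", and that the patient may be discontinued.

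SAP Appendix Table 2-1 assigns safety values to visits by days since the first dose: Days 2 to 43 for Week 4, Days 44 to 71 for Week 8, and Day 72 onward for Week 12. It has no cut-off at the last dose. If several values fall in one window, the latest is used. The PCS listings in 7.8.11.2 and 7.8.11.3 cover post-baseline values without naming the TE Period.

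**The concern.** A cut-off of 1 day after the last dose suits adverse events, which have a start date. It suits blood samples and vital signs less well, because these are taken only at visits. For a patient who stops before Week 4, the EOT Visit is the only scheduled post-baseline measurement. If it comes after a dose suspension, or is simply delayed, it can fall outside the TE Period.

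The reasons for suspension or discontinuation in Protocol 5.1.2.1 include volume depletion, electrolyte abnormalities, and clinically significant laboratory or vital-sign findings. Tables 2 and 3 of the SAP are built to show exactly these. Safety and tolerability are among the study's stated objectives, and Protocol 3.3 describes this as the first study of linaclotide in IBS-D. If one dose group has more early stopping, its PCS table could miss more of the relevant values than the placebo table does.

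**Working it through.** The documents state no figure for the PCS tables, so there is none to reproduce. The check is day arithmetic, followed by an illustration of size.

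**1. When is an EOT value counted?** Let L be the study day of the last dose, V the day of the EOT Visit, and k = V − L. The TE Period ends on Day L + 1, so the value counts if k ≤ 1 and is left out if k ≥ 2. The examples take Week 4 and Week 8 tests on their nominal days (29 and 57) and assume no unscheduled tests.

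| Last dose L | k | EOT day V | EOT value in PCS tables? | Scheduled TE assessments, including EOT | By-visit window |
|---|---|---|---|---|---|
| 20 | 1 | 21 | yes | 1 | Week 4 |
| 20 | 5 | 25 | no | 0 | Week 4 |
| 40 | 2 | 42 | no | 1 (Day 29) | Week 4 |
| 60 | 5 | 65 | no | 2 (Days 29, 57) | Week 8 |

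Only the second patient leaves the denominator. The third and fourth stay in, but their EOT result is not counted.

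**2. Do the outputs agree?** In the last three rows the EOT value falls in a by-visit window. In rows three and four it shares that window with the scheduled value (Days 29 and 42; Days 57 and 65). The latest-date rule then puts the EOT value in the by-visit summary, while the PCS table uses only the earlier one. As worded, the listing would show a PCS result at the EOT Visit that the table does not count.

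**3. Can k reach 2?** A suspension may last up to 5 days. If discontinuation is decided during or at the end of it, the last dose can precede the EOT Visit by 5 days or more. Protocol 6.3 does not cap the delay. The documents do not say how often this would happen.

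**4. Size, on assumed inputs.** The planned group size is 92 (Protocol 10.8, SAP 4). Assume a share d of 5% to 15% stops before the Week 4 tests, a share s of 50% to 100% of these is seen 2 or more days after the last dose, and none has an unscheduled TE value. Patients leaving the denominator = 92 × d × s:

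- low: 92 × 0.05 × 0.5 = 2.3, leaving 89.7
- high: 92 × 0.15 × 1.0 = 13.8, leaving 78.2

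**5. Effect on a percentage, also assumed.** Let all early stoppers be seen late (5, 9 or 14 patients, rounding 4.6, 9.2 and 13.8), let 3 of the remaining patients have a PCS value, and let every baseline be non-PCS.

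- TE Period only: 3/87 = 3.4%, 3/83 = 3.6%, 3/78 = 3.8%.
- EOT values counted, none of the early stoppers PCS: 3/92 = 3.3%.
- EOT values counted, 30% of the early stoppers PCS: from (3 + 1.5)/92 = 4.9% with 5 stoppers to (3 + 4.2)/92 = 7.8% with 14.

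The TE-only figure can therefore be slightly too high, about right, or about half of the figure with EOT values counted. Which applies depends on quantities that the documents do not give.

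**The case against.** There is a substantial case that little is lost.

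- Protocol 6.3 places the EOT procedures at the time of discontinuation. A patient seen on the day of the last dose or the next day is counted normally.
- Unscheduled tests are allowed at any time (Protocol 8.2.2). An abnormality that triggers suspension will often have been measured on drug or within a day of the last dose, which puts the patient in the denominator and, if PCS, in the numerator. Local laboratory results that change management must be recorded in the eCRF.
- An abnormality that leads to suspension or discontinuation is to be recorded as an adverse event (Protocol 8.2.1.2.3), and SAP 7.8.11.1 tabulates treatment-emergent events leading to discontinuation.
- Safety analysis is descriptive, so no test is affected. An on-treatment window is also a deliberate choice: Protocol 10.6.2 and 10.6.3 tabulate PCS values for the Treatment Period, and SAP Appendix 1 explains how that period was split.

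All of this stands, and it limits the likely size. It does not remove the gap. No rule brings a late EOT value into either PCS table, and a patient who stops early without an on-drug test has no other scheduled value.

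**Conclusion.** The point holds in a conditional form. As written, an EOT value taken 2 or more days after the last dose is not counted in either PCS table. A patient who stopped before the Week 4 tests leaves the denominator if, in addition, no unscheduled value falls in the TE Period. The by-visit summaries and the listing can then disagree with the PCS tables. Any bias of concern would be toward missing PCS values in groups with more early stopping. Its size is unknown and may be small; the 2.3 to 13.8 patients per group rest wholly on assumed rates.

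Three stronger readings might be inferred, and the documents do not support them.

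- *Early stoppers' EOT results are discarded.* They are left out of the PCS tables only, and only when late.
- *The PCS comparison becomes one among patients who tolerated the drug.* That would need late visits, no on-drug testing and unequal early stopping together, and none of these is documented.
- *Completers drop out as well.* They have Week 4 and Week 8 values, so they stay in the denominator. At most the Week 12 value is lost, if dosing ended 2 or more days before that visit. SAP Appendix Table 3-1 puts the usual last dose at Day 85, and Protocol 5.1.1.4 ties the last dosing day to the Week 12/EOT Visit. The Day 84 in Appendix Table 3-2 stands in a window-end entry and does not clearly give a last-dose day.

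**What to change.** In SAP 7.8.11.2 and 7.8.11.3, define a PCS post-baseline period that runs from the first dose to the later of 1 day after the last dose and the Week 12/EOT Visit, with unscheduled values included. Use it for numerator and denominator alike. State a maximum number of days after the last dose beyond which an EOT value is not counted, so that a sample taken long after stopping does not appear as a treatment-period finding. The documents give no basis for a particular number. It should be fixed before unblinding, and it must be longer than the 5-day suspension if it is to capture visits that follow one. Flag every value taken more than 1 day after the last dose in the listing, and say there that values beyond the maximum are listed but not tabulated. Keep the TE Period for adverse events, and record the change in SAP Appendix 1.

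The cost is SAP wording and programming, since the data are already collected. The downside is that a few counted values will come from days off drug; the flag makes these visible.

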7.8.11.3. Vital Signs

Descriptive statistics for vital signs (ie, pulse rate, systolic and diastolic BP, respiratory rate, temperature, and body weight) and changes from baseline at each visit and at the end of the period/study will be presented by treatment group.

The number and percentage of patients with PCS post-baseline vital signs will be tabulated by treatment group for the Treatment Emergent Period. A vital sign value will be considered PCS if it meets both the observed value criterion and the change from baseline value criterion. The criteria for PCS vital sign values is detailed in Table 3. The percentages will be calculated relative to the number of patients with available non-PCS baseline values and at least 1 assessment in the corresponding postbaseline period. The numerator will be the total number of patients with available baseline values and at least 1 PCS value in the corresponding post-baseline period. A supportive listing of patients with PCS post-baseline values will be provided, including the PID number, study center, and baseline and post-baseline values. A listing of all AEs for patients with PCS vital sign values will also be provided.

Table 3: Criteria for Potentially Clinically Significant Vital Signs

Parameter	Flag	Criteria^a	
		Observed Value	Change from Baseline
Sitting systolic blood pressure, mmHg	High	≥ 180	Increase of ≥ 20
	Low	≤ 90	Decrease of ≥ 20
Sitting diastolic blood pressure, mmHg	High	≥ 105	Increase of ≥ 15
	Low	≤ 50	Decrease of ≥ 15
Sitting pulse rate, bpm	High	≥ 120	Increase of ≥ 15
	Low	≤ 50	Decrease of ≥ 15
Weight, kg	High	—	Increase of $\geq 7\%$
	Low	—	Decrease of $\geq 7\%$

a A post-baseline value is considered potentially clinically significant if it meets both the observed-value and the change-from-baseline criteria.
 bpm=beats per minute.

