10.6.3 Vital Signs

Descriptive statistics for vital signs (ie, pulse rate, systolic and diastolic BP, respiratory rate, temperature, and body weight) and changes from baseline at each visit and at the end of the period/study will be presented by treatment group for the Treatment Period.

The number and percentage of patients with PCS post-baseline vital signs will be tabulated by treatment group for the Treatment Period. A vital sign value will be considered PCS if it meets both the observed value criterion and the change from baseline value criterion. The criteria for PCS vital sign values will be detailed in the SAP. The percentages will be calculated relative to the number of patients with baseline values and at least 1 assessment in the corresponding post-baseline period. The numerator will be the total number of patients with available non-PCS baseline values and at least 1 PCS value in the corresponding post-baseline period. A supportive listing of patients with PCS post-baseline values will be provided, including the PID number, study center, and baseline and post-baseline values. A listing of all AEs for patients with PCS vital sign values will also be provided.

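### The vital-sign PCS percentage restricts its denominator but not its numerator, baseline PCS status is undefined, and the MCH and MCHC limits cannot realistically be reached

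*SAP*

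**What the plan says.** **Vital signs, SAP 7.8.11.3.** Percentages are taken "relative to the number of patients with available non-PCS baseline values and at least 1 assessment in the corresponding postbaseline period". The next sentence reads: "The numerator will be the total number of patients with available baseline values and at least 1 PCS value in the corresponding post-baseline period". The first carries the non-PCS restriction; the second does not.

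**Vital signs, protocol 10.6.3.** The restriction sits on the other side. The denominator is "relative to the number of patients with baseline values and at least 1 assessment in the corresponding post-baseline period", and the numerator is the "total number of patients with available non-PCS baseline values and at least 1 PCS value in the corresponding post-baseline period". The protocol leaves the PCS vital-sign criteria to the SAP.

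**Laboratory values, SAP 7.8.11.2.** A non-PCS baseline is required both above and below the line.

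**What PCS means.** For vital signs, the Table 3 footnote says: "A post-baseline value is considered potentially clinically significant if it meets both the observed-value and the change-from-baseline criteria". Laboratory PCS (Table 2) depends on the observed value alone. In Table 3, weight has a dash for the observed value and a 7% change criterion in each direction.

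**Red-cell indices, Table 2.** Mean corpuscular hemoglobin (MCH) and "Mean corpuscular hemoglobin concentration" (MCHC) have a dash for the lower limit and > 3 x ULN for the upper. The neighbouring MCV row uses < 0.9 x LLN and > 1.1 x ULN.

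**Appendix 1 of the SAP**, which lists departures from the protocol, does not mention the vital-sign PCS rule.

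**The concern.** A percentage of patients with a newly abnormal value needs a numerator contained in its denominator. As worded, a patient excluded from the denominator for an abnormal baseline can still be counted in the numerator. The two documents also give different rules, neither of which matches the laboratory rule.

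Beneath this lies a gap in definition. The restriction depends on whether a baseline is PCS, but Table 3 defines PCS for post-baseline values and partly through change from baseline. A programmer has to decide what a non-PCS baseline is, and the table depends on that decision.

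The MCH and MCHC limits raise a different problem. A row that can never flag anyone shows 0% in each arm and looks like reassurance. Safety and tolerability are among the study's stated objectives, so these tables should be able to show what they claim to show.

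**Working it through.** Neither document states a PCS rate, so there is no figure to reproduce. The arm size of 92 comes from SAP section 4 and serves only to size an illustration.

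**1. Can a vital-sign baseline be PCS under the written rule?** Compared with itself, a baseline has a change of 0. Table 3 needs a change of at least 20 mmHg (systolic), 15 mmHg (diastolic) or 15 bpm (pulse). Checking every integer baseline from 20 to 300 for these three parameters found none that qualifies. Under the two-part rule, a non-PCS baseline is therefore any available baseline, and the restriction is void.

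**2. What if baseline is judged on the observed value alone?** This is an assumption; the SAP does not say it. Let N = 92, let k patients be beyond a limit at baseline and all be flagged later, and let x = 3 other patients be flagged.

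| Rule | Formula | k = 0 | k = 1 | k = 3 |
|---|---|---|---|---|
| SAP 7.8.11.3 | (x + k)/(N - k) | 3/92 = 3.26% | 4/91 = 4.40% | 6/89 = 6.74% |
| Restricted in both (laboratory form) | x/(N - k) | 3/92 = 3.26% | 3/91 = 3.30% | 3/89 = 3.37% |
| Protocol 10.6.3 | x/N | 3/92 = 3.26% | 3/92 = 3.26% | 3/92 = 3.26% |
| Unrestricted in both | (x + k)/N | 3/92 = 3.26% | 4/92 = 4.35% | 6/92 = 6.52% |

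The SAP form exceeds the laboratory form as soon as one such patient exists. It stays close to the unrestricted form, which is what step 1 yields, so most of the gap comes from whether these patients are counted at all.

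**3. How readily could k exceed 0?** Being flagged again in the same direction means worsening by the full change criterion. From a baseline exactly at the limit, that is:
- systolic: 180 + 20 = 200 or more, or 90 - 20 = 70 or less;
- diastolic: 105 + 15 = 120 or more, or 50 - 15 = 35 or less;
- pulse: 120 + 15 = 135 or more, or 50 - 15 = 35 or less.

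Such cases should be few.

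**4. MCH and MCHC.** The documents give no reference limits. Assume a ULN of 31-35 pg for MCH and 340-370 g/L for MCHC.
- Flag thresholds: 3 x 31 = 93 to 3 x 35 = 105 pg; 3 x 340 = 1,020 to 3 x 370 = 1,110 g/L.
- MCH (pg) = MCV (fL) x MCHC (g/L)/1000. At an MCHC of 360 g/L, an MCH of 93-105 pg needs an MCV of 93/0.36 = 258 to 105/0.36 = 292 fL. The SAP's own high-MCV flag starts at 1.1 x 95 = 104.5 to 1.1 x 105 = 115.5 fL (assumed MCV ULN 95-105 fL).
- MCHC = hemoglobin/hematocrit. With hemoglobin at its high flag and hematocrit at its low flag together (assumed hemoglobin ULN 175 g/L, hematocrit LLN 0.36), MCHC = (1.1 x 175)/(0.9 x 0.36) = 192.5/0.324 = 594 g/L, well short of 1,020.

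The high flags are out of practical reach and there is no low flag. The other rows with this pattern are basophil, eosinophil and monocyte counts, which can triple; red-cell indices cannot. Table 2 has 18 chemistry and 13 hematology rows, so 2 of 31 are affected.

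**5. Weight.** If the dash means that no observed-value limit applies, an 80 kg patient is flagged at 80 x 1.07 = 85.6 kg or more, or at 80 x 0.93 = 74.4 kg or less. The row works.

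**The case against.** The strongest reply is step 1: if no baseline can be PCS, the two patient sets coincide and the mismatch changes no percentage. That is right for the rule as written, and it limits the point. It does not remove it. The SAP would then contain a restriction that does nothing, and a programmer who tries to make it work would probably judge baseline on the observed value, which is the reading on which the numerator stops being a subset.

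A second reply is that little depends on these tables. Safety analyses are descriptive. Patients with PCS values are listed with baseline and post-baseline values and with their AEs. Values and changes are summarized for every laboratory parameter. Hemoglobin, hematocrit, MCV and red cell count keep limits in both directions. All of this stands and keeps the severity low, but it does not make a row that always reads 0% informative.

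A reader might also infer more than the documents support:
- **That the weight row can flag no one, because both criteria are required.** This holds only on a hyper-literal reading. A dash in Table 2 marks a limit that does not apply, and the same reading is natural in Table 3.
- **That the mismatch biases the comparison between arms.** Nothing in the documents suggests that patients with out-of-limit baselines would be unevenly distributed.
- **That correcting it makes the percentages smaller.** Not necessarily. If 3 patients with in-limit baselines are flagged and 4 unflagged out-of-limit patients are removed, 3/92 = 3.3% becomes 3/88 = 3.4%.

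**Conclusion.** The point holds, as a minor one. The vital-sign rule is inconsistent within the SAP, reverses the protocol without being listed as a change, and rests on a baseline status that the SAP does not define. Under the written two-part rule the effect on the percentages is nil. If baseline is judged on the observed value alone, one affected patient in an arm of 92 moves the figure from 3.3% to 4.4%; the numbers of patients are illustrative.

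The MCH and MCHC rows will read 0% in every arm. This rests on assumed reference limits, but the distance is large enough that no plausible laboratory ULN would change the conclusion.

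It would go too far to call the safety tables wrong as written. The weight row works on its ordinary reading, 29 of the 31 laboratory rows are not in question here, and no hypothesis test is affected.

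**What to change.** 1. In SAP 7.8.11.3, use one set of patients above and below the line, and state how baseline PCS status is judged. If a new-onset rate is intended, one option is to require a baseline within the Table 3 observed-value limits in both places. If every worsening is to count, drop the restriction from both. Whether patients who start beyond a limit and then worsen should count is the sponsor's choice, and it should be written down.
2. List the departure from protocol 10.6.3 in Appendix 1.
3. In Table 2, replace the MCH and MCHC limits with attainable two-sided limits, for example in the form already used for MCV, with the sponsor confirming the multiples.
4. As a clarification only, footnote Table 3 to say that weight is PCS on the change criterion alone. Since weight has no observed limit on which to judge a baseline, all patients with a baseline and a post-baseline weight would enter that row.

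The cost is a few lines of SAP text and the matching program specifications. No new data are needed. The vital-sign percentages may move slightly in either direction, and the MCH and MCHC rows become able to show something.
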